15. Client Satisfaction Questionnaire (CSQ) (Attkisson et al. 1982) is an 8-item unidimensional measure of client satisfaction with services. Psychometric properties, operating characteristics, and coefficient alpha (.93) are very strong for this measure which we will collect from adolescents and parents.
16. Decision Making Involvement Scale (DMIS) (Miller et al., 2012): is a 30-item scale to measure adolescent involvement in a decision. The five subscales are: “Child Seek” (child asks for an opinion or information from parent), “Child Express” (child expresses an opinion or information to parent), “Parent Seek” (parent expresses advice or opinion to child), “Parent Express” (parent expresses advice or opinion to child), and “Joint/Options” (negotiation or brainstorming between parent and child). We will collect this measure from adolescents and parents.

DATA ANALYSIS

Hypothesis testing:

Each hypothesis examines part of the mechanism underpinning intervention impact on medication continuity.

Hypothesis #1: Adolescents will use greater than 80% of relevant intervention components. For each subject, we will calculate the proportion of **recommended** intervention components that were utilized by the subject during the study intervention period. The mean and 95% confidence interval (CI) will be computed to give a range estimate of the fidelity measure. To evaluate our hypothesis, we will utilize the computed CI to determine if 80% or greater is a plausible value, such that if the CI includes a value of 80% or greater we will reject the null hypothesis. We will also examine the temporal distribution of use for each of the recommended components.

Hypothesis #2: Use of the intervention components will be related to improvements in the targeted UTBC factors. Using a generalized linear model, we will test whether the intervention addressed the UTBC factors (i.e., pre-intention factor scales and ABMS/PBMS total and subscale scores). Model predictors will include a fixed effect indicator of time point (baseline or end of study). A significant effect of time point in the expected direction would indicate UTBC factor improvement.

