Hypothesis #3: Medication continuity will be higher at the end of the study compared to the baseline period. We will compare the percentage of days covered with medicine using a paired t-test. In exploratory analyses, we will compare this cohort's percentage of days covered at end of study with the percentage of days covered in a control group that is accruing as part of another study (IRB# 2020-0236).

Hypothesis #4: Pre-post changes in UTBC factors will be related to increases in medication continuity. We will calculate the change score for each relevant UTBC factor (end of study minus baseline) and the change score for medication continuity (end of study minus baseline). We will model the association between change in UTBC factor scores (independent variable) with change in medication continuity (dependent variable) using generalized linear model. A significant effect of change in UTBC factor scores (beta coefficient) in the expected direction would indicate changes in UTBC factor scores were associated with medication continuity improvement.

Exploratory analyses:

We will conduct descriptive analyses to characterize rates of diversion at baseline and end of study using a McNemar's test to see if rates differ. We will summarize responses to the client satisfaction questionnaire descriptively as this may facilitate future dissemination.

Power and Sample Size:

We are adequately powered for our exploratory analysis of Hypothesis #3. The study would require a sample size of 18 for each group (i.e. a total sample size of 36), to achieve a power of 80% and a level of significance of .05 (two sided), to detect a difference in means between the intervention and the control groups of 15.7% (i.e. 66.2% vs. 50.5%) on the percentage of days covered with medicine assuming a pooled standard deviation of 16.5. Due to the low intra-class correlations observed in previous studies of ADHD medication continuity (ICC = 0; [name] et al. 2018), the analyses will not account for the nesting of patients within physicians. We will recruit 44 patients (22 in this cohort and 22 in control group from 2020-0236) to ensure that 36 are retained for this analysis. A retention rate of 80% (36/44) is conservative in light of the 12-month retention rate of 92% achieved by [name] in his current trial.

Scientific Rigor:

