2.3.3 Secondary outcome analyses

- Change in pre-intention factors of Unified Theory of Behavior Change at baseline and approximately 4 months later.

The dependent variable will be the change in adolescent and parent self-report of pre-intention factors. Items were reported using a 5- or 7-point scale, depending on the item, which was then re-scaled to a 5-point scale for ease of interpretation.

- Change in intention to take/give ADHD medicine regularly at baseline and approximately 4 months later.

The dependent variable will be the change in the intention to take/give ADHD medicine. Items were reported using a 7-point scale, which were then re-scaled to be on a 5-point scale for ease of interpretation.

- Change in adolescent-report of medication barriers at baseline and approximately 4 months later.

The dependent variable will be the change in adolescent-report of medication barriers. Items were reverse coded so that higher scores mean less barriers.

- Change in parent-report of medication barriers at baseline and approximately 4 months later.

The dependent variable will be the change in parent-report of medication barriers. Items were reverse coded so that higher scores mean less barriers.

- Change in medication diversion at baseline and approximately 4 months later.

The dependent variable will be the change in medication diversion.

- Change in Decision Making Involvement Scale at baseline and approximately 4 months later.

The dependent variable will be the change in parent and adolescent-report of the Decision Making Involvement Scale subscale scores.

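### The only test stated for Hypothesis #2 has no within-person term, and it cannot be fitted to the change scores that the SAP makes the outcome

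*Protocol*

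**What the plan says.** Protocol, Data Analysis, Hypothesis #2: "Using a generalized linear model, we will test whether the intervention addressed the UTBC factors". The factors are the pre-intention scales and the total and subscale scores of the two barrier scales. On the form of the model: "Model predictors will include a fixed effect indicator of time point (baseline or end of study"). The decision rule is: "A significant effect of time point in the expected direction would indicate UTBC factor improvement". No other predictor is named, and nothing is said about how the two scores from one person are linked.

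The same part of the protocol does state the pairing elsewhere. For Hypothesis #3: "We will compare the percentage of days covered with medicine using a paired t-test". Hypothesis #4 uses change scores, and diversion is compared with McNemar's test. Power and Sample Size deals with one kind of dependence, saying that "the analyses will not account for the nesting of patients within physicians", but is silent on repeated scores within a person.

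The SAP is dated 5/19/2022 and the protocol 2/21/2021. SAP 2.3.3 says of the pre-intention factors: "The dependent variable will be the change in adolescent and parent self-report of pre-intention factors". For the barrier scales it says "The dependent variable will be the change in adolescent-report of medication barriers" and "The dependent variable will be the change in parent-report of medication barriers". It names no model, test or confidence interval for any of them.

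**The concern.** Time point can be a predictor only if each person contributes two rows, one per survey. With time point alone in the model, the residual variance contains all the stable differences between people, which cancel when each person is compared with himself or herself. For positively correlated scores the reported standard error is then too large, the interval too wide and the p-value too high.

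Protocol, Scientific Rigor, says that the trial is an initial examination of whether the intervention engages the mechanism and so deserves a larger trial. Hypothesis #2 is the direct test of change in those factors. With about 20 participants, a needlessly conservative test could lead to a report of no engagement where there was some.

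The SAP does not settle the matter. It changes the outcome to one row per person, which removes the protocol's predictor, and puts no test in its place.

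**Working it through.** **The plan's own figure.** The only power calculation is for the exploratory between-group comparison under Hypothesis #3: a difference of 15.7 points, SD 16.5, 80% power, two-sided 0.05. It reproduces. The normal-approximation formula gives 18 per group (power 81.4%), and the noncentral t gives 79.2% at 18. It has no bearing on Hypothesis #2, for which the documents give no power, effect size or pre-post correlation.

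**Can the protocol model be run on the SAP outcome?** The protocol outcome is the score, with two rows per person and time point = baseline or end. The SAP outcome is end minus baseline, with one row per person. In the second data set time point does not vary, so its coefficient cannot be estimated. What remains is a test of whether mean change is zero, that is, a paired t-test, which the SAP does not state.

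**Inputs for the size of the effect.**
- n = 20 (Protocol, Study Design; SAP section 1). The protocol's Procedures and Power sections say 22; about 18 (36/2) are expected to be retained. All three were run.
- Two-sided 0.05: assumed here, as the documents state it only for the Hypothesis #3 comparison.
- r = 0.3, 0.5, 0.7, a change of 0.5 SD, equal SDs at both times, and a normal outcome with identity link: all assumed.

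**Standard errors, in SD units.**
- Correct SE of the mean change: sqrt(2(1-r)/n).
- SE from a model with time point alone: sqrt(2/n), on average.
- Ratio: 1/sqrt(1-r).

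For n = 20 the second is sqrt(2/20) = 0.316. The first is sqrt(1.4/20) = 0.265, sqrt(1.0/20) = 0.224 and sqrt(0.6/20) = 0.173 at r = 0.3, 0.5 and 0.7. The ratios are 1.20, 1.41 and 1.83.

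**Power.** Paired power comes from the noncentral t with n-1 = 19 degrees of freedom and noncentrality 0.5/SE = 1.89, 2.24 and 2.89. Power and type I error of the time-point model come from 100,000 simulated trials per setting, using an unpaired pooled-variance t with 2n-2 = 38 degrees of freedom.

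| r | Paired power | Time-point model | Share of power lost | Type I error, time-point model |
|---|---|---|---|---|
| 0.3 | 43.4% | 31.3% | 1 - 31.3/43.4 = 28% | 2.1% |
| 0.5 | 56.5% | 28.5% | 1 - 28.5/56.5 = 50% | 0.8% |
| 0.7 | 78.2% | 24.7% | 1 - 24.7/78.2 = 68% | 0.1% |

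**Sensitivity.**
- Sample size: at r = 0.5 and 0.5 SD, power falls from 51.8% to 24.8% with n = 18 and from 60.9% to 32.4% with n = 22.
- Larger effect: at 0.8 SD and n = 20, it falls from 81.8% to 72.5% (r = 0.3), 92.5% to 75.5% (r = 0.5) and 99.2% to 80.4% (r = 0.7).
- Effect set so that the paired test has 80% power at n = 20: the time-point model has 70%, 54% and 27% at r = 0.3, 0.5 and 0.7.

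**The case against.** A reader might infer that the plan treats the two scores as independent. The documents do not say so. The protocol lists what the predictors will include, which need not be everything in the model, and it is silent on covariance. Since the other pre-post comparisons in the protocol are paired or use change scores, the investigators may well have intended a subject term. What is established is that no such term is stated, not that an unpaired analysis is planned.

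A reader might also infer that the test loses most of its power. That holds only towards the top of the assumed range of r. At r = 0.3 the loss is about a quarter, and with a 0.8 SD change it is smaller throughout. The documents supply no figure that would select one case.

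The strongest point on the other side is the SAP. It is later, it presents itself as the detailed account of the analyses, and its change-score outcome already uses the pairing. An analyst who follows it and tests mean change against zero will not meet the inflated standard error. That stands, and it makes the loss conditional. It does not close the point, because the SAP neither names that test nor withdraws the protocol's model and decision rule. Any error would also be conservative, with no excess of false positives, in a small early study.

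Finally, Hypothesis #2 is worded as a relation between use of the components and improvement. A pre-post test contains no measure of use. That is equally true of the protocol's model and of the fix below.

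**Conclusion.** The point holds in conditional form. The one stated test for Hypothesis #2 gives too large a standard error if fitted as written, by 1/sqrt(1-r) for positively correlated scores. It also does not fit the outcome that the SAP defines, and the SAP supplies no replacement.

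With 20 pairs and a 0.5 SD change, roughly a quarter, a half or two-thirds of the power would be lost at r = 0.3, 0.5 or 0.7. Those sizes rest on assumed values of r and of the effect, and on equal SDs. The direction rests only on r being positive, and the mismatch between the two documents needs no assumption at all. The point calls for a correction to the SAP and does not suggest a flaw in the data collected.

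**What to change.** In SAP 2.3.3, name one paired analysis for each factor. Two suitable forms are a paired t-test on change, or the equivalent linear mixed model with time point fixed and subject random. Choose one, report the mean change with its 95% CI, and state that it replaces the generalized linear model under the protocol's Hypothesis #2.

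The SAP should also say that this tests pre-post change only. If the relation between component use and improvement is to be tested, that needs its own stated analysis with use as a predictor.

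The cost of the main change is a few sentences in the SAP and about a line of SAS code. No new data are needed.

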9. Fidelity to intended use of intervention components: For each adolescent and parent, we will calculate the proportion of intervention components completed relative to the components that were recommended by the portal based on adolescent/parent responses to the assessment battery. For intervention components that are used once (e.g. trial on/off medicine), we will identify a portal data element to characterize intervention component completion. For intervention components that are used more than once (e.g. refill reminders, pill taking reminders, etc.), we will define "intended use" of the feature as use for at least 2 months since research suggests that, on average, it takes 2 months to develop a new habit (Lally et al. 2010). Mehealth for ADHD will capture and report on these data elements to characterize fidelity to the intended use of intervention components for each adolescent and parent.
10. Pre-intention factors of UTBC influencing medication continuity (Appendix G & H): Our measurement strategy for the adolescent and parent pre-intention factors closely follow well-developed procedures (Ajzen et al. 1981). We will use standard scales that have been used in hundreds of previous studies using the UTBC and closely related basic science theories. For example, an item to assess social norms would be "Most of the people who are important to me think I should take ADHD medicine regularly." Responses are on a 7-point scale from strongly agree (+3) to strongly disagree (-3). The internal consistency of items within each construct is good ($0.7 \leq \alpha \leq 0.9$) (Steele et al. 2005; Bentley et al. 2009; Cornelio et al. 2009; Boyko et al. 2011). For this study, we will assess pre-intention factors (i.e. expectations, social norms, self-concept/image, affect and emotions, and self-efficacy) framed around the behavior of "taking ADHD medicine regularly" following published methods (Francis et al. 2004) and informed by our prior qualitative research ([name] et al. 2009, 2012).

11. Behavioral Intentions (Appendix I & J): Teen and parent intention for teen to take ADHD medicine regularly will be measured using the standard measure of intention from the UTBC (Ajzen and Fishbein, 1981).

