12. Implementation factors of UTBC influencing medication continuity (Appendix K & L): These factors will be measured using the Adolescent and Parent Medication Barriers Scales (AMBS and PMBS) (Simons et al. 2007; Simons et al. 2010). Adolescents and parents respond using a 5-point Likert-like scale from “strongly disagree” to “strongly agree” to report perceived barriers to medication taking. Both the adolescent scale (17-items) and parent scale (16-items) have strong internal consistency for total score and the four factor-analytically derived subscales: ‘Disease frustration/adolescent issues’, ‘Regimen adaptation/cognitive’, ‘Ingestion issues’, and ‘Parent reminder’. For criterion-related validity, adolescents classified as non-adherent had significantly higher barrier scores than those classified as adherent. In prospective validation studies, the adolescent-perceived barriers of ‘Disease frustration/adolescent issues’ and parent-perceived barriers of ‘Regimen adaptation/cognitive issues’ were associated with poorer adherence to medication taking (Simons et al. 2010).
13. Medication Continuity: We will calculate the percentage of days covered with medicine based pharmacy dispensing records and verified by parent report of ADHD service use using the reliable Services for Children & Adolescents – Parent Interview (Eaton Hoagwood et al. 2004). This measures ADHD service use, including office visits and medication use. We have successfully obtained pharmacy dispensing records via parental permission for 95% (155/164) of subjects across 2 studies (R01 MH074770, K23 MH083027) ([name] et al. 2013; [name] et al. 2016). Pharmacy dispensing records provide an objective, unobtrusive, reliable measure that is a well-accepted proxy for medication consumption (Steiner et al. 1997) that was significantly correlated with the more expensive and invasive Medication Event Monitoring System (MEMSCap™) which uses a microprocessor in the medication container cap to record the day and time of each vial opening (Farley et al. 2003).
14. Medication Diversion: Self-report of giving away, trading, or selling ADHD medicine to someone for whom it was not prescribed will be collected via a confidential web-based survey used in past population-based studies of middle/high school students. (Boyd et al. 2007; McCabe et al. 2011a).

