Official Title of the study: **Web Based Tools to Improve Medication Continuity in Adolescents With ADHD**

NCT number: **NCT04173000**

Document name: **Statistical Analysis Plan**

Date of the document: **5/19/2022**

The results of the Web Based Tools study will be assessed as described in this document. This statistical analysis plan begins with an overview of the key components of the study, including its design, objectives, and outcomes measures. This is followed by a detailed description of the statistical analyses that will be utilized to address study hypotheses.

1. Overview of study: This study is a 4-month open label trial to test whether an intervention engages the mechanism underlying medication continuity and improves outcomes. Adolescents and their parents that agree to participate in the study will receive the intervention (MeHealth for ADHD software with medication continuity tools). We planned to enroll a total of 20 adolescents aged 11-15 with ADHD with poor medication continuity who receive care from one of the 24 pediatricians recruited from ~8 practices who currently use the MeHealth for ADHD portal.

1.1 Study Objective: Test a multi-component intervention that systematically identifies and targets aspects of the Unified Theory of Behavior Change (UTBC) model most relevant for each adolescent with poor ADHD medication continuity.

Working hypothesis 1: Medication continuity will be higher at the end of the study compared to the baseline period.

Working hypothesis 2: Use of the intervention components will be related to improved outcomes as measured by change in the Unified Theory of Behavior Change factors.

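### Protocol Hypotheses 2 and 4 each test up to about 20 UTBC scores under a per-test significance rule, with no adjustment, order within the set, required number of positive scores or exploratory label.

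*Protocol*

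**What the plan says.** Protocol, DATA ANALYSIS, Hypothesis #2 fits a generalized linear model with a time-point effect to the "pre-intention factor scales and ABMS/PBMS total and subscale scores". The claim rule follows: "A significant effect of time point in the expected direction would indicate UTBC factor improvement".

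Hypothesis #4 relates change in these scores to change in days covered: "We will calculate the change score for each relevant UTBC factor (end of study minus baseline"; the factors that count as relevant are not listed. A significant coefficient "in the expected direction would indicate changes in UTBC factor scores were associated with medication continuity improvement".

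Both hypotheses stand under the protocol's hypothesis-testing heading. A separate exploratory heading covers only diversion and satisfaction.

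The SAP ranks outcomes in 1.2: days covered is the sole primary, and the UTBC changes are secondary. Its second working hypothesis in 1.1 reads "Use of the intervention components will be related to improved outcomes as measured by change in the Unified Theory of Behavior Change factors". SAP 2.3.3 defines the change variables but gives no test, significance level or claim rule for them, and the SAP does not carry Hypothesis #4.

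**The concern.** Under Scientific Rigor, the protocol justifies the open-label design as a first look at whether the intervention engages the mechanism and so merits a larger trial. Hypotheses #2 and #4 carry much of that argument, and they are tested before and after treatment in about 20 adolescents with no concurrent control.

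With many scores, a per-test rule and no statement of how the results combine, a favourable result on one scale could be reported as mechanism engagement. In Hypothesis #4 the unlisted set of relevant factors leaves a further choice open. The SAP is dated 5/19/2022, after the study end date of 5/24/21 in its section 2.2.2, and still does not list them.

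**Working it through.** **The plan's own figure.** The only calculation stated is for the exploratory two-group comparison of days covered: difference 15.7, SD 16.5, two-sided 0.05, power 80%, 18 per group. The normal approximation gives n = 2 × (1.960 + 0.842)² × (16.5/15.7)² = 2 × 7.85 × 1.104 = 17.3, so 18. It reproduces, but it sets no error rate for Hypotheses #2 or #4.

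**Count of scores.**
- Pre-intention (Outcome measures, item 10): the factors are "expectations, social norms, self-concept/image, affect and emotions, and self-efficacy", which is 5. The section covers both reporters ("Our measurement strategy for the adolescent and parent pre-intention factors closely follow well-developed procedures"), so 5 × 2 = 10.
- Barriers (item 12): each of the adolescent and parent scales (AMBS, PMBS) has "strong internal consistency for total score and the four factor-analytically derived subscales", so (1 + 4) × 2 = 10.
- Protocol total for Hypothesis #2: 10 + 10 = 20. For Hypothesis #4 this is an upper count.
- SAP reading: 1.2 and 2.3.3 list one adolescent and one parent barrier outcome. With the same 10 pre-intention scores, 10 + 2 = 12.
- Not counted, but at the same secondary tier of the SAP: intention (2 scores) and Decision Making Involvement (5 subscales × 2 reporters = 10).

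One joint model for Hypothesis #4 would not avoid the issue. Twenty slopes and an intercept on 22 adolescents leave 22 − 21 = 1 residual degree of freedom. In practice these are separate or selected tests.

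**Error rate with no true effect.** Two-sided 0.05 gives 0.025 per test in the favourable direction. With independent tests, P(at least one) = 1 − 0.975^k: 1 − 0.975^20 = 0.397 and 1 − 0.975^12 = 0.262. For a common correlation ρ between test statistics, the normal integral 1 − ∫ φ(u) Φ((1.960 − √ρ·u)/√(1 − ρ))^k du gives:

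| ρ | 12 tests | 20 tests |
|---|---|---|
| 0 | 26.2% | 39.7% |
| 0.3 | 20.2% | 28.0% |
| 0.5 | 16.0% | 21.0% |
| 0.8 | 9.3% | 11.2% |

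Checks for 20 tests at ρ = 0.5:
- Simulated paired t-tests at n = 18, 20 and 22 give about 22.4%.
- Building each barrier total from its four subscales gives 21.1%.
- Separate regressions for Hypothesis #4 at n = 20 give 21% to 22%.
- A favourable result in either hypothesis, simulated together, occurs in about 39% (about 64% at ρ = 0).

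**If pairing is ignored in Hypothesis #2.** The protocol names only a fixed time effect. If within-person correlation is left out, each test is conservative. At between-score correlation 0.5 and n = 20, the 20-test rate falls to about 13% (pre-post correlation 0.25) or 4% to 5% (0.5). Hypothesis #4 uses change scores and is not affected.

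**The case against.** The strongest reply is that the protocol contains no rule under which any one score counts as mechanism support. Hypothesis #2 can be read factor by factor, each significant result supporting a claim about that factor at its own nominal error. That stands: a reader might infer an any-one-counts rule, but the documents are silent on how the results combine. The defect is that silence.

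Three other stronger readings also fail.
- A reader might take 21% as the false-positive rate. It is one cell of the table. The correlation of 0.5 appears in neither document, the 0.05 level is stated only for the days-covered comparison, and the figure needs correctly sized tests and refers to one hypothesis at a time.
- A reader might say the plan has no hierarchy. The SAP does rank days covered above the UTBC changes; what is missing is an order within the UTBC set.
- A reader might apply 20 tests throughout. The later SAP supports about 12, and the protocol does not list the factors for Hypothesis #4.

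It is also fair to say that a small single-arm pilot need not control family-wise error. That is a reason to label the family exploratory. It does not justify keeping claim rules tied to significance under a hypothesis-testing heading.

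**Conclusion.** The point holds as a gap in the plan that should be closed. It is not a flaw in the primary analysis: days covered is a single primary outcome and is unaffected.

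Each hypothesis tests up to about 20 scores (about 12 on the SAP's barrier outcomes), and nothing written prevents a mechanism claim from one. Against 2.5% for one test, the chance of a favourable significant result with no true effect is about 11% to 40% per hypothesis for 20 tests and 9% to 26% for 12. Even the lowest value in the table, 9.3%, is more than three times nominal. These figures assume two-sided 0.05, correlations from 0.8 down to 0, all scores tested and correctly sized tests. If pairing is ignored, the Hypothesis #2 rate is lower.

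**What to change.** In protocol Hypotheses #2 and #4 and SAP 2.3.3:

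1. Label the UTBC factor, barrier, intention and Decision Making Involvement analyses exploratory.
2. Report every score with its estimate and 95% CI.
3. Replace the two claim rules with a statement that no claim of mechanism engagement, or of association with continuity, will rest on a single unadjusted p-value.

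If a formal claim is wanted, list the factors for Hypothesis #4 and apply Holm over all scores tested within each hypothesis. This is safer than naming a few key scores now, because that choice would be made after the study end date. Holm within each hypothesis does not control the combined rate over both, and the text should say so.

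The cost is wording, with no new data. The exploratory label gives up a confirmatory mechanism claim. With Holm over 20 scores the first step is at 0.05/20 = 0.0025. At n = 20 and 80% power, the detectable paired change in Hypothesis #2 (noncentral t) then rises from about 0.66 to 0.98 SD. For Hypothesis #4, by Fisher's z, the detectable correlation rises from tanh((1.960 + 0.842)/√17) = 0.59 to tanh((3.023 + 0.842)/√17) = 0.73.
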